## **B. Adequacy of Protection Against Risks**

**Informed Consent and Assent.** Prior to the start of the school year, and after a successful run-in, information regarding the study will be sent out to all families in randomized schools. They will also be invited to attend an information night to learn about the study in detail. Information about the study will also be visible in the school newsletter prior to the start of recruitment, posted on school websites and posters displayed at the school to invite students to participate in the study. The project will ask from the school administration staff the first and last name of students, grade and teacher in order to create individualize recruitment packets. Students will receive a recruitment packet from their teacher to be sent home with their daily schoolwork. The packet will include information about the study, child and adult caregiver assent and consent to participate in the study. We will obtain assent and consent from parents of children in the schools. This assent and consent will be for all the study assessments during the entire study period.

For the students consented to participate in assessment, study staff will identify a series of after school times for students to complete the baseline survey. Student and adult caregivers who are not able to attend an assessment session after school, will be provided the opportunity to conduct the assessment at their home or place of their choosing.

**Protections Against Risk.** All individuals who participate in the surveys will be told that they can decline to answer any specific questions. All will be told they can stop participation at any time. Any paper records will be kept in a locked cabinet for up to three years.

Confidentiality of the study participants will be protected in this project. All participants will be assigned a study identification (ID) number. Information linking the participant name and study ID number is kept in a password protected computer file, separate from the survey responses and other data collected in the study. Access to the linked data is under the oversight of the Joint PIs, [name], at the NMSU-ASC, Farmington and [name] of the FHCRC, who are responsible for maintaining the confidentiality. Questionnaire data is coded and managed as data files in a separate, protected part of the computer network. No information is released that could lead to the identification of any participating individual. Access to computer-stored information will require simultaneous knowledge of the data format, computer language, file name, and password. No individuals will be identified in any reports from the study.

We regard the risk of participation in this project as relatively slight. We will take care that every interviewer/facilitator is trained to handle an adverse situation sensitively and empathically, if a participant does experience significant distress during focus groups, interviews, or questionnaire completion. We will be prepared to consult with our IRB and/or human resources in the event that an adverse situation is reported. All participants will be given the name and number of a person in IRB to contact if an adverse situation should arise.

In the school gardens, participants will receive training in appropriate use of garden tools and be encouraged to wear appropriate attire.

**Vulnerable Subjects.** The individual level, school level, family level and community level intervention focuses on improving health of children and their parent/caregiver by integrating healthy eating and gardening throughout Shiprock, NM and Tsaile, AZ area. While the study is considered minimal risk, it is understood that permission to participate in the study means the agreement of parent or guardian to the participation of their child.

The institutional review board at the Fred Hutchinson Cancer Research Center has strict guidelines regarding the participation of children in research. All policies and recommendations will be followed. The IRB will approve all mechanisms for soliciting the assent of the children and the permission of their parents or guardians.

### **C. Potential Benefits of the Proposed Research to Participants and Others**

Many aspects of the proposed study may be beneficial to the participants and their families. Benefits may include learning about healthy eating and how to garden, greater communication about healthy meals among families, gaining satisfaction knowing that they are providing information that may help other people within the Navajo community and their families in the future.

### **D. Importance of Knowledge to be Gained**

This study will provide important information about preparation, storage, health benefits of foods and using school gardens to improve the vegetable and fruit consumption and general health among people of the Navajo Nation. Given the broad engagement with the school communities in project, our hope is that the schools and families involved will also become health champions in their communities, passing on their knowledge of healthy eating and gardening to others in their community and encouraging participation in our future studies. The project also serves to maintain an important relationship between the Navajo Nation tribal leaders and the NMSU ASC for their other collaborative research projects. This relationship makes it possible for us to sustain our efforts with our Navajo partners and provides a mechanism to transfer research findings directly to Navajo Nation policy makers.

The knowledge gained will lay the groundwork for an R01 type proposal, including specification of both the intervention and outcome measures, that would formally evaluate intervention effectiveness of the intervention using an experimental design.

## **E. Data Safety Monitoring Plan**

This plan pertains to the intervention activities involving the garden. The risk of intervention activities is small due to the modest levels of exertion of the proposed project and the care in implementation of all gardening activities. Anticipated risks, if any, may include minor strain injuries sustained while being physically active. At the end of each class, staff will ask participants if they have experienced any muscle soreness or strains or other concerns. The research staff will record positive responses. The research staff will carry a first aid kit to all events to attend to any minor bruises, cuts or other injuries experienced by youth. Each week the research staff will send a report to the PIs. The PIs will track the concerns/problems and assess for any patterns that might emerge. If a trend or pattern emerges, the PIs will consult with the FHCRC IRB and adjustments to the program will be made accordingly.

Should any adverse event occur, the staff monitoring the intervention will inform the Community field manager within the hour. The community field manager will inform the PI of any adverse event within 24 hours. The PI will file an adverse event form with FHCRC IRB. The PI will send a copy of an adverse event report submitted to the FHCRC IRB to the NIH within 48 hours. We will track expected and adverse research related events and monitor over time.

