**Healthy Eating and Gardening Curriculum.** We will provide schools with our curriculum (developed and implemented in our current pilot study) for both healthy eating and gardening that covers the entire school year. Each content area consists of 12 lessons throughout the year and coordinated with the growing season (See Tables 4 & 5, total of 24 lessons). Lessons will be scheduled based on input from school staff, but will occur approximately two times per month. The curriculum was designed based on both formative research with the target population, previous school garden interventions, investigator expertise in theory-based interventions to promote healthy eating and gardening, and instructional design. The curriculum draws on Social Cognitive Theory, which posits that self-efficacy and observational learning are critical for promoting self-regulation and maintaining healthy behaviors. The curriculum meets N.M state standards in health education, science, and

social studies for grades 3 and 4. By integrating the lessons into regular classroom activities, the interventionist can also help with required student assessment (i.e. pre/post learning) demonstrating growth relative to the state standards.

Lessons will be co-led by our interventionist and a teacher from the school as part of the regular school day, consisting of about 45 minutes for each lesson. Our curriculum is focused on children in third and fourth grade. Lessons will be implemented for both grade groups on the same day, but at different times, according to the teachers' schedules. This will allow for smaller groups and a lower teacher to student ratio.

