The interviewer-administered questionnaires will be completed online with questions constructed from items taken from the IRB approved previous study, “Engaging School and Family in Navajo Gardening for Health” and valid measures adapted minimally to be culturally relevant and understood by children and adult members of the Navajo community. The questionnaire for children will include healthy eating behaviors and gardening participation and self-efficacy including fruit and vegetable consumption at meals, relative frequency of health foods, gardening participation, and gardening self-efficacy. The parent/caregiver questionnaire will include dietary intake questions, fruit and vegetable consumption using the instrument from the 5 A Day study, as well as soda and fast food consumption, obesity related dietary behaviors and gardening frequency measures. Both parent and child will complete a virtual picture sort frequency method following the approached used in our current study. (originally developed in an African American community and modified for this study using foods commonly consumed by Navajo). Weekly frequencies will be converted to a relative healthy food ratio (healthy foods to total foods) based on the Alternative Healthy Eating Index (AHEI) categories.

There are minimal risks associated with participating in the survey assessments. It is possible that some participants (adult or child) may experience discomfort when answering questions about their health behavior. Participants will be informed that they do not have to answer any questions that make them feel uncomfortable. Finally, risks may include feelings of embarrassment, for children, during body measurements (height and weight). All staff will be trained to be aware of such discomfort, how to react in this situation, how to ease participants, and provide outside resources when needed.

As a physical out-door activity, the act of gardening can occasionally produce risks including cuts, scrapes, and sunburn. In most circumstances, accidents occurring in a garden are superficial. When proper precautions are taken (i.e. wearing appropriate footwear, sunscreen, hat, gloves) and training is given on the appropriate use of tools, accidents are usually preventable. Participants will be informed of the risk of out of door activities and advised to wear appropriate clothing, sunscreen and hat and to drink plenty of water.

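### The only solicited safety question is asked as each class ends, with no look-back period, so sunburn and later soreness may be under-recorded

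*Combined protocol and SAP*

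**What the plan says.** Section V.E (Data Safety Monitoring Plan) covers the garden activities. Its active safety check is a single question: "At the end of each class, staff will ask participants if they have experienced any muscle soreness or strains or other concerns". Staff record positive answers, and "Each week the research staff will send a report to the PIs". The investigators look through these reports for trends; if one appears, they consult the institutional review board and adjust the program.

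The expected effects are named in two places:
- Section V.A (Risks to Human Subjects) says that "the act of gardening can occasionally produce risks including cuts, scrapes, and sunburn".
- Section V.E says: "Anticipated risks, if any, may include minor strain injuries sustained while being physically active". It also has staff carry a first aid kit "to attend to any minor bruises, cuts or other injuries experienced by youth".

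The timetable is in section IV.A, under the Healthy Eating and Gardening Curriculum. Lessons are part of the school day, "consisting of about 45 minutes for each lesson". On frequency: "Lessons will be scheduled based on input from school staff, but will occur approximately two times per month". On number: "Each content area consists of 12 lessons throughout the year and coordinated with the growing season", which makes 24 lessons over the two content areas.

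Two passive routes exist besides the question. Section V.E has staff escalate any adverse event within the hour, whenever it comes to light. Section V.B gives every participant a review-board contact.

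**The concern.** The question comes when a lesson of about 45 minutes has just finished. An effect that develops later that day cannot be reported then. Sunburn is the clearest case: section V.A expects it, yet the question does not mention it, so it can surface only under the open item on other concerns. Muscle soreness is named in the question, but some of it may also develop after class.

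The question recurs at the next class, but with no stated reference period. Nothing tells staff to ask children aged 8 to 11 about the days in between.

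At stake is the completeness of the safety record. Section V.E makes review-board consultation and program changes depend on a pattern in the weekly reports. If one class of expected effect is recorded less completely than the others, that trigger is less sensitive to it. Only positive answers are recorded, so a count arrives without the number of children asked. Attendance on the observer checklist (section IV.D) gives only a partial denominator.

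**Working it through.** The plan gives no safety figure to reproduce: no event rate, onset time or expected count. The check compares the passages and adds simple arithmetic on spacing and exposure.

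**1. Is there any other solicited safety question?** The teacher and observer checklists (section IV.D) cover content delivered, attendance, participation, logistics and preparation; no safety item is listed. The T1 to T3 measures (section V.A) are behavioral questionnaires plus height and weight; again none is listed. The end-of-class question is the only one described.

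**2. Which named effects can the question catch when it is asked?**

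| Effect | Where named | Can be apparent by the end of the lesson? |
|---|---|---|
| Cut | V.A, V.E | Yes |
| Scrape | V.A | Yes |
| Bruise | V.E (first aid) | Yes |
| Strain during activity | V.E | Yes |
| Sunburn | V.A | Possibly not (assumption) |
| Muscle soreness | V.E (in the question) | Some possibly not (assumption) |

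Four of six types can be apparent in class and two may not be. This counts types, not events.

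**3. How long until the question is asked again?**
- Stated rate of two lessons a month: 365 / (2 × 12) = 15.2 days.
- 24 lessons over about 10 months (August to June, about 304 days): 304 / 24 = 12.7 days.
- If the question is asked only after the 12 gardening lessons, as the garden scope of section V.E would allow: 304 / 12 = 25.3 days.

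The gap is therefore about 13 to 15 days, or about 25 days on the narrower reading. It is longer for a child who misses a class.

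**4. How much exposure is involved?** Child-lessons = gardening lessons × children per school × intervention schools in the first year.
- 80 children per school (section V.A, assumed attained): 12 × 80 × 2 = 1,920.
- Lower eligibility limit of 40 (section III.D): 12 × 40 × 2 = 960.
- Upper eligibility limit of 100: 12 × 100 × 2 = 2,400.

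These figures assume that all 12 gardening lessons are held. The COVID-19 context in section IV.B reports schools closed for the rest of that year, so actual exposure may be lower. They measure the exposure to which the question applies; they do not estimate missed events.

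**The case against.** The strongest case on the other side is that the existing question already works for most of what is expected, and that its wording is open. Section V.E anticipates strain that occurs during activity, not delayed soreness. A teacher and an interventionist lead each lesson and a data collector observes, so cuts, scrapes and bruises would be seen. The question sets no limit to that day's class and invites any other concern, so a child could mention last week's sunburn at the next lesson. The adverse-event pathway and the review-board contact are not tied to the end of class. The risk is described as small, section V.A lists preventive measures such as sunscreen, hats and gloves, and no endpoint uses the count.

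Most of this stands, and it limits the point to delayed effects. It does not remove it. Open wording permits a look-back but does not direct one, and recall over about two weeks is likely to be incomplete at this age. The staff pathway begins only when staff see or hear of an event, and the review-board contact requires a family to call; a mild sunburn is unlikely to prompt that.

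A reader might also infer that a child hurt in one class and absent from the next is never asked. The documents do not support that: the child is asked at the end of the class where the injury occurred and again at the next class attended. What is missing is an instruction to cover the interval.

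**Conclusion.** The point holds in a limited form. The only solicited safety question has no stated look-back period and omits an effect the protocol itself anticipates, so sunburn and some muscle soreness may be under-recorded in the weekly reports.

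This rests on one assumption from outside the documents: that these two effects can appear hours after exposure. That is plausible for sunburn and for some soreness. It should not be extended to strains sustained in class.

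A reader might infer that the monitoring will miss most of the anticipated effects. The documents do not support that: most of the named types can be apparent in class, and without event rates no share of events can be calculated. Nor do they show that a low count would be taken as proof of safety, because no safety endpoint or safety conclusion is planned.

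The consequence is a less complete safety record and a somewhat less sensitive trigger for review. The point is minor, and the primary outcomes and their analysis are unaffected.

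**What to change.** In section V.E, keep the end-of-class question for immediate injuries. Add one question at the start of each class, asking about any soreness, strain, cut, sunburn or other concern since the child last attended. Anchoring it to the child's own last attendance also covers children who missed a class. Record the number of children asked alongside the positive answers, so that the weekly reports carry a denominator.

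The cost is about a minute of class time and one line on the lesson checklist. The recorded event count may rise slightly because ascertainment is more complete; the weekly reports should say so when the question is introduced.

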## **VI. LIST OF STUDY DOCUMENTS**

### **A. Participant Recruitment & Enrollment**

1. Parent Consent – approved 8/31/19
2. Youth Assent – approved 8/31/2018
3. Parent Consent 2 – approved 3/29/19
4. Parent Consent 3 – approved 7/11/2019
5. Youth Assent 2 – approved 7/11/2019
6. Parent Consent 4 – approved 9/05/2019
7. Youth Assent 3 – approved 9/05/2019
8. Parent Verbal Consent – 01/16/20

### **B. Assessment**

1. Baseline Questionnaire – approved 8/31/2018
2. Parent/Guardian Baseline Questionnaire – approved 7/3/19
3. Family Survey – approved 7/3/19
4. 3rd and 4th grade Student Baseline Questionnaire – approved 7/3/19
5. Baseline Questionnaire (T1) – Parent/Child electronic survey – approved 8/12/19
6. Follow Up Questionnaire (T2) – approved 01/16/20

### **C. Study Approach Documents & Intervention**

1. School Information Sheet – approved 7/3/19
2. Assessment Overview Document – approved 7/3/19
3. Recruitment packet documents – approved 7/3/19
  - a. Intervention Later Information Sheet
  - b. Intervention NOW Information Sheet
  - c. Parent Instruction Sheet
4. Study Logo – approved 7/11/2019
5. Principal Support Letter template – approved 7/11/2019
6. Intervention Curriculum – approved 8/12/19

7. Follow up Assessment Parent/Guardian Postcard – approved 01/16/20
8. Follow up Assessment Child/Student Postcard – approved 01/16/20
9. Follow up Assessment Parent/Guardian Call Script – approved 01/16/20
10. Revised Intervention Curriculum Part I – approved 1/28/20
11. Revised Intervention Curriculum Part II – approved 3/12/20
12. Family Update Letter – COVID-19 – approved 3/19/20

